4.4.2 Secondary Efficacy Variables

Secondary efficacy variables of the study are listed below.

4.4.2.1 Number of bleeding sites at Week 12

Number of bleeding sites will be calculated as the number of sites with a BI of 1 or 2. Summary statistics for number of bleeding sites by visit and treatment will be provided ([Table 14.2.2.2](#)).

4.4.2.2 MGI score at Week 12

The modified gingival index (MGI) will be assessed on the facial and lingual surfaces of each scorable tooth (7-7 in each arch). Two scores will be recorded buccally/labially (papilla and margin) and two scores lingually/palatally (papilla and margin). The scoring of the MGI will be performed under dental office conditions using a standard dental light for illuminating the oral cavity. The MGI scoring system will be as follows:

0 = absence of inflammation

1 = mild inflammation; slight change in color, little change in color; little change in texture of any portion of the marginal or papillary gingival unit.

2 = mild inflammation; criteria as above but involving the entire marginal or papillar gingival unit.

3 = moderate inflammation; glazing, redness, edema, and/or hypertrophy of the marginal or papillary gingival unit.

4 = severe inflammation; marked redness, edema and/or hypertrophy of the marginal or papillary gingival unit, spontaneous bleeding, congestion, or ulceration.

The study examiner will assess and record the modified MGI for each site. MGI score of a subject will be calculated as the mean MGI over all tooth sites. Summary statistics for MGI score by visit and treatment will be provided ([Table 14.2.3.2](#)).

4.4.2.3 Overall plaque score and interproximal plaque score at Week 12

The plaque index (PI) will be assessed on the facial and lingual surfaces of each scorable tooth (7-7 in each arch). Three scores should be recorded buccally/ labially (distal, body, mesial sites) and three scores lingually/ palatally (distal, body, mesial sites). Disclosed plaque will be scored as follows:

0 = No plaque

1 = Slight flecks of plaque at the cervical margin of the tooth

2 = A thin continuous band of plaque (1mm or smaller) at the cervical margin of the tooth

3 = A band of plaque wider than 1mm but covering less than 1/3 of the area

4 = Plaque covering at least 1/3 but less than 2/3 of the area

5 = Plaque covering 2/3 or more of the crown of the tooth.

The study examiner will assess and record the plaque index for each site. Overall plaque score and interproximal plaque score will be calculated as the mean PI over all tooth sites and mean PI over interproximal sites (distal and mesial) respectively. Summary statistics for overall and interproximal plaque score by visit and treatment will be provided ([Table 14.2.4.2](#), [Table 14.2.5.2](#)).

4.4.3 Exploratory Efficacy Variables

Exploratory variables of the study are listed below.

4.4.3.1 BI score at Week 6

BI score will be calculated in the same way as stated in Section 4.4.1.1.

4.4.3.2 Number of bleeding sites at Week 6

Number of bleeding sites will be calculated in the same way as stated in Section 4.4.2.1.

4.4.3.3 MGI score at Week 6

MGI score will be calculated in the same way as stated in Section 4.4.2.2.

4.4.3.4 Overall plaque score and interproximal plaque score at Week 6

Overall plaque score and interproximal plaque score will be calculated in the same way as stated in Section 4.4.2.3.

4.4.4 Handling of Missing Values/Censoring/Discontinuations

Missing data will not be replaced or imputed. Dropouts will be included in analyzes up to the point of discontinuation.

4.5 Analysis of Secondary Objectives

Number of bleeding sites will be analyzed using ANCOVA model with treatment, gender, smoking status and baseline MGI stratification as factors and baseline score as covariate. Adjusted means of two treatments and treatment difference will be provided together with 95% CI and P-values ([Table 14.2.2.1](#)).

MGI score will be analyzed using ANCOVA model with treatment, gender, smoking status as factors and baseline score as covariate. As baseline MGI is included as covariate, baseline MGI stratification will not be included in the model. Adjusted means of two treatments and treatment difference will be provided together with 95%CI and P-values ([Table 14.2.3.1](#)).

Overall plaque score and interproximal plaque score will be analyzed using the same ANCOVA model with treatment, gender, smoking status and baseline MGI stratification as factors and baseline score as covariate. Adjusted means of two treatments and treatment differences will be provided together with 95%CIs and P-values ([Table 14.2.4.1](#), [Table 14.2.5.1](#)).

4.6 Analysis of Exploratory Objectives

All exploratory variables will be summarized by visit and treatment. The same ANCOVA models as in Section 4.4.1.2 and Section 4.5 will be applied to corresponding variables of Week 6.

4.7 Analysis of Safety

4.7.1 Adverse Events and Serious Adverse Events

All safety data will be reported for the Safety population as per actual treatment received. All subjects screened will be included in the list of AEs.

AE will be regarded as treatment emergent if they occur on or after the start date and time of the first treatment usage (as determined by start date and time from the EXPOSURE/dispensing panel; if this date is missing a suitable alternative will be used eg date and time of randomization). All other AEs prior to this will be considered non-treatment emergent.

All AEs will be reviewed by Clinical Research prior to database freeze and will be coded using the Medical Dictionary for Regulatory Activities (MedDRA). During this review stage, AEs will be further categorized as oral or non-oral.

The following summary tables and listings will be presented by treatment group.

- Table of treatment emergent AEs by SOC and Preferred Term ([Table 14.3.1.1](#))
- Table of treatment emergent AEs by Oral/Non-Oral and Preferred Term ([Table 14.3.1.2](#))
- Table of Treatment emergent treatment related AEs by Oral/Non-Oral and Preferred Term ([Table 14.3.1.3](#))
- Listing of all AEs (including all subjects: [Listing 16.2.7.1](#) for all randomized subjects; [Listing 16.2.7.2](#) for non-randomized subjects)
- Listing of death ([Listing 14.3.2.1](#))
- Listing of non-fatal SAEs ([Listing 14.3.2.2](#))
- Listing of treatment emergent AEs leading to withdrawal ([Listing 14.3.2.3](#))
- Listing of treatment emergent AEs classified as oral ([Listing 14.3.2.4](#))

In the event that there is nothing to report a null listing will be produced.

4.7.2 Other Safety Variables

All incidents captured in the study will be listed ([Listing 16.2.7.3](#)). A null listing will be provided if there is no incident reported.

4.8 Analysis of Other Variables

A number of subjects will have repeated plaque index (PI) or gingivitis index (MGI) assessments conducted by the examiner. The repeat assessments will be compared to the original assessments separately for PI and MGI. The repeat assessments will not be used in any efficacy analysis. The first and second assessments on each tooth at a given visit will be cross-tabulated and a weighted Kappa coefficient (κ) will be calculated, along with the 95% confidence interval, to assess the intra-examiner repeatability ([Table 14.2.6](#) and [Table 14.2.7](#)). Repeatability will be deemed

- Excellent, if $\kappa > 0.75$
- Fair to good, if $0.4 \leq \kappa \leq 0.75$
- Poor if $\kappa < 0.4$

All subjects who have repeatability data will be included in this analysis. SAS PROC FREQ will be used for this analysis with codes similar to the following:

GlaxoSmithKline Consumer Healthcare Confidential

```
PROC FREQ DATA = INTRA;  
TABLES R1*R2/AGREE (wt = fc);  
RUN;
```

Where R1 = first assessment score by an assessor, R2 = second (repeat) assessment score by an assessor.

5 Changes to the Protocol Defined Statistical Analysis Plan

There is no change to the planned statistical analysis specified in the protocol version 5.0 [(Dated: 05/Apr/2017)].

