6.2.3. Modified Gingival Index (MGI) Assessment (Lobene, 1986)

The MGI assessment is a non-invasive evaluation which focuses on the visual symptoms of gingivitis (for example, redness, texture, edema). The MGI will be assessed on the facial and lingual surfaces of each scorable tooth (7-7 in each arch). Two scores will be recorded buccally/labially (papilla and margin) and two scores lingually/palatally (papilla and margin). The scoring of the MGI will be performed under dental office conditions using a standard dental light for illuminating the oral cavity.

The MGI scoring system will be as follows:

0 = absence of inflammation

1 = mild inflammation; slight change in color, little change in color; little change in texture of any portion of the marginal or papillary gingival unit.

2 = mild inflammation; criteria as above but involving the entire marginal or papillary gingival unit.

3 = moderate inflammation; glazing, redness, edema, and/or hypertrophy of the marginal or papillary gingival unit.

4 = severe inflammation; marked redness, edema and/or hypertrophy of the marginal or papillary gingival unit, spontaneous bleeding, congestion, or ulceration.

The MGI will be assessed by the same examiner on all evaluable teeth at Baseline/Visit 2, Visit 3 and Visit 4.

Repeatability Exercise

Data for MGI assessments will be taken from replicate examinations performed by the Examiner during the study. Depending on subject visit scheduling, every effort

Document Name	207014 protocol		
Type	Version	Document Identifier	Effective Date
eldo_clinical_doc	5.0; Most-Recent; Effective; CURRENT	090032d580d1fee8	05-Apr-2017 13:38:03
Reason For Issue	Auto Issue		

will be made to do repeatability examinations during each session, that is, one in the morning and one in afternoon every day examinations are carried out.

Repeatability examinations will have a minimum of 10 minutes between and, where possible, will be separated by another subject.

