9.3.5. Repeatability Analysis

A number of subjects will have repeat gingivitis (MGI and TPI) assessments conducted by the examiner. The repeat assessments will be compared to the original assessments. The repeat assessments will not be used in any efficacy analysis. The purpose of repeated assessments is to check the consistency of the examiner. As each subject will provide around 100 records for repeatability judgement, one subject on the morning and one subject in the afternoon in each visit day over the course of the study is sufficient for repeatability assessment. The first and second assessments on each tooth at a given visit will be cross-tabulated and a weighted Kappa coefficient (κ) will be calculated, along with the 95% confidence interval, to assess the intra-examiner repeatability. Repeatability will be deemed [Fleiss]:

- Excellent, if $\kappa > 0.75$
- Fair to good, if $0.4 \leq \kappa \geq 0.75$
- Poor if $\kappa < 0.4$

All subjects who have repeatability data will be included in this analysis.

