Week 6	LSmean (SE) [1]	x.xx (x.xxx)		x.xx (x.xxx)	
	Comparison [1][2]	Difference	95% CI	P-value	%Diff[3]
	Test Dentifrice vs Reference Dentifrice	x.xx	(x.xx, x.xx)	0.xxxx	xx.x
Week 12	Same as above				

[1] From ANCOVA with treatment, gender, smoking status and baseline MGI stratification as factors and baseline as covariate.

[2] Difference is the first named treatment minus second named treatment such that a negative difference favors the first named treatment.

[3] Percentage difference calculated as (treatment difference/adjusted mean of reference treatment)*100%.

PPD

Programming Note: For Table 14.2.3.2, please update footnote [1] as

[1] From ANCOVA with treatment, gender, smoking status as factors and baseline as covariate.

Protocol 207014

Program Run Date:xxxx

Table 14.2.1.2
Summary of Bleeding Index Score
Intent-to-Treat Population

Intent-to-Treat Population (N=XX)

Visit		Test Dentifrice (N=XX)	Reference Dentifrice (N=XX)	Overall (N=XXX)
Baseline	n	Xx	xx	xx
	MEAN	x.xx	x.xx	x.xx
	SD	x.xxx	x.xxx	x.xxx
	SE	x.xxx	x.xxx	x.xxx
	MEDIAN	x.xx	x.xx	x.xx
	MINIMUM	X.xx	x.xx	x.xx
	MaxIMUM	X.xx	x.xx	x.xx
Week 6	n	Xx	xx	
	MEAN	x.xx	x.xx	
	SD	x.xxx	x.xxx	
	SE	x.xxx	x.xxx	
	MEDIAN	x.x	x.x	
	MINIMUM	X.x	x.x	
	MAXIMUM	X.x	x.x	
Week 12	Same as above			

Protocol 207014

Program Run Date:xxxx

Table 14.2.6
 Repeatability for Modified Gingival Index
 Repeatability Population

Repeatability Population (N=XX)

	Repeated	Missing	0	1	2	3	4
Initial							
Missing		xx	xx	xx	xx	xx	xx
0		xx	xx	xx	xx	xx	xx
1		xx	xx	xx	xx	xx	xx
2		xx	xx	xx	xx	xx	xx
3		xx	xx	xx	xx	xx	xx
4		xx	xx	xx	xx	xx	xx
Kappa	0.xx						
95% CI	(0.xx, 0.xx)						

MGI Score

0: Absence of inflammation; 1: Mild inflammation; slight change in color, little change in color, little change in texture of any portion of marginal or papillary gingival unit; 2: Mild inflammation; criteria as above but involving the entire marginal or papillary gingival unit; 3: Moderate inflammation; glazing, redness, edema and/or hypertrophy of marginal or papillary gingival unit; 4: Severe inflammation; marked redness, edema and/or hypertrophy of marginal or papillary gingival unit, spontaneous bleeding, congestion, or ulceration.

Programming Note: For Table 14.2.5.2, use PI score descriptions in footnote.

Oral Health

207014

Statistical Reporting and Analysis Plan Amendment 1, 19 Jan 2018

Protocol 207014

Program Run Date:xxxx

Table 14.3.1.1
Treatment Emergent Adverse Event by System Organ Class and Preferred Term

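### The 95% CI for the repeatability kappa treats some 100 sites in one mouth as independent, so it is too narrow whenever agreement varies between examinations

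*SAP*

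**What the plan says.** SAP section 4.8 compares repeat with original scores separately for MGI and PI: "The first and second assessments on each tooth at a given visit will be cross-tabulated", and a weighted kappa is reported "along with the 95% confidence interval, to assess the intra-examiner repeatability". The code offered is "TABLES R1*R2/AGREE (wt = fc", that is, Fleiss-Cohen weights on a plain two-way table. It has no subject, examination or visit identifier. The shell in SAP Attachment 2 (Table 14.2.6, "Repeatability for Modified Gingival Index") is one pooled 0-4 by 0-4 table with one kappa and one interval.

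The records come from many sites in each mouth. For MGI, Protocol 6.2.3 states: "Two scores will be recorded buccally/labially (papilla and margin) and two scores lingually/palatally (papilla and margin". Protocol 6.2.5 takes six PI scores per tooth. Protocol 9.3.5 reasons from the site count: "As each subject will provide around 100 records for repeatability judgement", and on that ground it regards "one subject on the morning and one subject in the afternoon in each visit day" as sufficient. Protocol 9.2.1 admits to the repeatability population anyone with a repeat at any visit, so one subject may contribute several examinations.

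Neither document mentions clustering, a subject-level bootstrap, a cluster-adjusted variance or a kappa per examination.

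**The concern.** The confidence limits from the AGREE option are large-sample limits for independent rows. Here the rows come in blocks. All pairs from one mouth share the same two sittings, the same lighting, the same state and recall of the examiner, and the same level of disease. If the examiner is more consistent in some examinations than in others, the information depends mainly on the number of examinations, while the formula counts sites.

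Kappa for MGI and PI is a listed objective, and each index is scored by one examiner throughout. BI has no repeatability exercise (Protocol 6.2.4), so these two kappas are the only planned quantitative evidence of examiner consistency. An interval that is too tight can appear to exclude the 0.75 or 0.40 boundary when the real uncertainty includes it.

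**Working it through.** **1. Records per mouth.** Protocol 4.1 requires at least 20 teeth, and scoring 7-7 in each arch gives at most 28.

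- MGI, 4 scores per tooth: 20 × 4 = 80 to 28 × 4 = 112. This range contains the protocol's own figure of about 100.
- PI, 6 scores per tooth: 20 × 6 = 120 to 28 × 6 = 168.

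**2. Design effect.** With m pairs per mouth and intraclass correlation ICC of agreement within an examination, the variance is multiplied by 1 + (m − 1) × ICC, and the interval width by its square root. This is an approximation for kappa. The ICC is not in the documents and is assumed. For m = 100 and ICC 0.02: 1 + 99 × 0.02 = 2.98, and √2.98 = 1.73.

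Factor by which the planned interval would have to be widened:

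| Pairs per mouth | ICC 0 | ICC 0.01 | ICC 0.02 | ICC 0.05 | ICC 0.10 |
|---|---|---|---|---|---|
| 80 | 1.00 | 1.34 | 1.61 | 2.22 | 2.98 |
| 100 | 1.00 | 1.41 | 1.73 | 2.44 | 3.30 |
| 112 | 1.00 | 1.45 | 1.79 | 2.56 | 3.48 |
| 168 | 1.00 | 1.63 | 2.08 | 3.06 | 4.21 |

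**3. Simulation with a varying disagreement rate.** Assumptions: five categories; site-score probabilities 0.02, 0.18, 0.58, 0.20 and 0.02; 100 sites per mouth; 20% of repeat scores (the median rate where it varies) moved by one category, up or down; Fleiss-Cohen weights; 3,000 runs per scenario; 10, 20, 40 or 60 examinations (the total is not stated in the documents). A logit SD of 0.5 means that examinations one SD either side of the median disagree at about 13% and 29% of sites (logit 0.20 = −1.386; −1.386 ± 0.5 back-transforms to 0.132 and 0.292). A logit SD of 1.0 gives about 8% and 40%.

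| What varies between examinations | Kappa | Planned SE, 20 exams | True SE, 20 exams | SE ratio, 10-60 exams | Coverage, 10-60 exams |
|---|---|---|---|---|---|
| Nothing | 0.844 | 0.0079 | 0.0079 | 1.00-1.03 | 94.5-95.0% |
| Mean score of the mouth only | 0.864 | 0.0070 | 0.0089 | 1.24-1.27 | 87.5-88.4% |
| Disagreement rate, logit SD 0.5 | 0.837 | 0.0080 | 0.0145 | 1.78-1.81 | 72.2-72.7% |
| Both of the above | 0.857 | 0.0072 | 0.0141 | 1.92-2.01 | 66.8-69.2% |
| Disagreement rate, logit SD 1.0 | 0.819 | 0.0084 | 0.0243 | 2.90-2.93 | 49.0-50.0% |

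Going from 10 to 60 examinations shrinks both SEs but does not restore coverage. The second row shows that variation in disease level between mouths is enough to make the limits too narrow, even with a constant disagreement rate.

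**4. Simulation with a shared calibration shift.** Here each repeat examination carries a common shift on the 0-4 scale, with 112 MGI sites per mouth. With 20 or 40 mouths and 1,500 runs, shift SDs of 0.10, 0.15 and 0.20 gave SE ratios of about 1.1, 1.3 and 1.65 and coverage of about 92%, 87% and 77-78%; with no shift, coverage was 94%. A separate run with 20 mouths and site-level rating noise of SD 0.2 gave ratios of 1.06, 1.27 and 1.52 and coverage of 93%, 89% and 78%. With noisier ratings (SD 0.3 to 0.5, kappa about 0.58 to 0.74) the ratios fell to 0.95-1.03, 0.97-1.08 and 1.03-1.23, because independent noise then dominates the shared part.

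**The case against.** The best case for leaving the plan alone is that nothing depends on the interval. Both documents attach the labels excellent, fair to good and poor to kappa itself, the proposed change leaves that estimate as it is, and repeat scores enter no efficacy analysis. The objective is the last in the list, and the primary endpoint, BI, is not covered by it. All of this stands. It limits the consequence.

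The absolute change may also be small. In the noisier shift scenarios the planned half-width was about 0.014 to 0.027, and the largest shift changed it by at most about 0.004. A reader's conclusion would then change only if kappa fell very close to a cut-off. This also stands for that model. Where the disagreement rate varies between examinations, the change is larger (see the verdict). The documents do not say which model is nearer the truth.

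Two points concern the reading. The text cross-tabulates by tooth, not by site. Site level is the natural reading, because scores are recorded by site and the shell uses raw 0-4 categories. Records by tooth would still be clustered: with m = 28, ICC 0.05 gives √(1 + 27 × 0.05) = √2.35 = 1.53. The code is also offered only as an example. That permits a clustered method, but none is specified.

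Finally, the protocol's remark about 100 records is a practical justification, not a formal precision calculation. That is fair, but it shows the same counting of sites as independent units.

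**Conclusion.** The concern holds. As written, the 95% interval is valid only if site pairs within a mouth behave as independent observations; otherwise it is too narrow. With no clustering, the planned limits cover 94-95% and need no correction.

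The direction is certain and the size is not, because the ICC, the rating noise and the number of repeat examinations are all assumed. Over the assumptions tried, the true SE ranged from about equal to the planned SE to about 2.9 times it, and coverage from about 95% down to about 50%. In absolute terms, for 20 examinations of 100 sites, the half-width goes from 1.96 × 0.0080 = 0.016 to 1.96 × 0.0145 = 0.028 at logit SD 0.5, and from 1.96 × 0.0084 = 0.016 to 1.96 × 0.0243 = 0.048 at logit SD 1.0. The planned factor could be further off for PI, which has up to 168 pairs per mouth.

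This should be corrected, because the plan chose to report a 95% interval for a listed objective. It does not threaten the kappa estimates, the repeatability labels or any efficacy result.

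**What to change.** In SAP section 4.8, keep the Fleiss-Cohen weighted kappa from the pooled table as the point estimate and replace the source of the interval. Suggested text:

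> The 95% confidence interval for each weighted kappa will be obtained by a bootstrap that resamples subjects with replacement, keeping all repeat examinations and all sites of a subject together. The independence-based limits from PROC FREQ will not be reported.

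A subject-level jackknife or another cluster-robust SE is an equal alternative. If few subjects are re-examined, a jackknife with t limits on the number of subjects minus one is the safer choice. In Tables 14.2.6 and 14.2.7, show the numbers of subjects, repeat examinations and site pairs, and state that the unit cross-tabulated is the site.

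The cost is one or two sentences and a short macro. No new data are needed and the point estimate does not change. The interval will usually be wider; if there is no clustering it will be about the same as now.

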Attachment 1: List of Data Displays

Study XXXX_List of
Outputs.xlsx

Attachment 2: Template for Tables, Figures and Listings

This is a guideline which will give the guidance of treatment labels that will be used for the table header and in the figures, listings and in the footnotes.

The treatment labels for the column heading will be as follow:

- Test Dentifrice
- Reference Dentifrice

Add following footnote to all TLFs.

Test Dentifrice: Experimental dentifrice containing 0.454% w/w stannous fluoride & 0.0721% w/w sodium fluoride

Reference Dentifrice: Regular fluoride dentifrice containing 0.14% w/w sodium monofluorophosphate.

Oral Health

207014

Statistical Reporting and Analysis Plan Amendment 1, 19 Jan 2018

Protocol 207014

Program Run Date:xxxx

Table 14.1.1
Subject Disposition
All Screened Subjects

All Screened Subjects (N=xxx)

	Test Dentifrice N (%)	Reference Dentifrice N (%)	Overall N (%)
TOTAL SUBJECTS SCREENED			xxx
SUBJECTS NOT RANDOMIZED			xxx (xx.x)
DID NOT MEET STUDY CRITERIA			xxx (xx.x)
ADVERSE EVENT			Xxx (xx.x)
LOST TO FOLLOW UP			xxx (xx.x)
PROTOCOL VIOLATION			Xxx (xx.x)
WITHDRAWAL OF CONSENT			Xxx (xx.x)
OTHER			Xxx (xx.x)
SUBJECTS RANDOMIZED	xxx	xxx	xxx
COMPLETED STUDY	xxx (xx.x)	xxx (xx.x)	xxx (xx.x)
DID NOT COMPLETE STUDY	xxx (xx.x)	xxx (xx.x)	xxx (xx.x)
DID NOT MEET STUDY CRITERIA	xxx (xx.x)	xxx (xx.x)	xxx (xx.x)
ADVERSE EVENT	xxx (xx.x)	xxx (xx.x)	xxx (xx.x)
LOST TO FOLLOW-UP	xxx (xx.x)	xxx (xx.x)	xxx (xx.x)
PROTOCOL VIOLATION	xxx (xx.x)	xxx (xx.x)	xxx (xx.x)
WITHDRAWAL OF CONSENT	xxx (xx.x)	xxx (xx.x)	xxx (xx.x)

	Test Dentifrice N (%)	Reference Dentifrice N (%)	Overall N (%)
OTHER	xxx (xx.x)	xxx (xx.x)	xxx (xx.x)
SAFETY POPULATION	xxx (xx.x)	xxx (xx.x)	xxx (xx.x)
ITT POPULATION	xxx (xx.x)	xxx (xx.x)	xxx (xx.x)
PP POPULATION	xxx (xx.x)	xxx (xx.x)	xxx (xx.x)

Percentages for non-randomized category are based on number of screened subjects; percentages for randomized category are based on number of randomized subjects

Oral Health

207014

Statistical Reporting and Analysis Plan Amendment 1, 19 Jan 2018

Protocol 207014

Program Run Date:xxxx

Table 14.1.2
Analysis Population
All Randomized Subjects

Randomized Population (N=xxx)

	Test Dentifrice N (%)	Reference Dentifrice N (%)	Overall N (%)
SUBJECTS EXCLUDED FROM SAFETY POPULATION	xxx (xx.x)	xxx (xx.x)	xxx (xx.x)
REASON 1	xxx (xx.x)	xxx (xx.x)	xxx (xx.x)
REASON 2	xxx (xx.x)	xxx (xx.x)	xxx (xx.x)
...			
SUBJECTS EXCLUDED FROM ITT POPULATION	xxx (xx.x)	xxx (xx.x)	xxx (xx.x)
REASON 1	xxx (xx.x)	xxx (xx.x)	xxx (xx.x)
REASON 2	xxx (xx.x)	xxx (xx.x)	xxx (xx.x)
...			
SUBJECTS WITH AT LEAST ONE DATA POINT EXCLUDED FROM PP ANALYSIS	xxx (xx.x)	xxx (xx.x)	xxx (xx.x)
SUBJECTS COMPLETELY EXCLUDED FROM PP POPULATION	xxx (xx.x)	xxx (xx.x)	xxx (xx.x)
PROTOCOL DEVIATIONS LEADING TO EXCLUSION FROM PP			
ALL VISITS			

	Test Dentifrice		Reference Dentifrice		Overall	
	N	(%)	N	(%)	N	(%)
DEVIATION 1	xxx	(xx.x)	xxx	(xx.x)	xxx	(xx.x)
DEVIATION 2	xxx	(xx.x)	xxx	(xx.x)	xxx	(xx.x)
...						
WEEK2						
DEVIATION 3	xxx	(xx.x)	xxx	(xx.x)	xxx	(xx.x)
DEVIATION 4	xxx	(xx.x)	xxx	(xx.x)	xxx	(xx.x)
...						
WEEK4						
DEVIATION 5	xxx	(xx.x)	xxx	(xx.x)	xxx	(xx.x)
DEVIATION 6	xxx	(xx.x)	xxx	(xx.x)	xxx	(xx.x)
...						

Oral Health

207014

Statistical Reporting and Analysis Plan Amendment 1, 19 Jan 2018

Protocol 207014

Program Run Date:xxxx

Table 14.1.3.1
Subject Demographics and Baseline Characteristics
Safety Population

Safety Population (N=XX)

	Test Dentifrice (N=XX)	Reference Dentifrice (N=XX)	Overall (N=XX)
SEX n (%)			
MALE	xx (xx.x)	xx (xx.x)	xx (xx.x)
FEMALE	xx (xx.x)	xx (xx.x)	xx (xx.x)
RACE n (%)			
ASIAN	xx (xx.x)	xx (xx.x)	xx (xx.x)
BLACK or AFRICAN	xx (xx.x)	xx (xx.x)	xx (xx.x)
AMERICAN INDIAN OR ALASKA NATIVE	xx (xx.x)	xx (xx.x)	xx (xx.x)
NATIVE HAWAIIAN OR OTHER PACIFIC ISLANDER	xx (xx.x)	xx (xx.x)	xx (xx.x)
WHITE	xx (xx.x)	xx (xx.x)	xx (xx.x)
MULTIPLE	xx (xx.x)	xx (xx.x)	xx (xx.x)
AGE (YEARS)			
n	XX	XX	XX
MEAN	XX.X	XX.X	XX.X
SD	XX.XX	XX.XX	XX.XX
MEDIAN	XX.X	XX.X	XX.X
MINIMUM	XX	XX	XX

Oral Health

207014

Statistical Reporting and Analysis Plan Amendment 1, 19 Jan 2018

	Test Dentifrice (N=XX)	Reference Dentifrice (N=XX)	Overall (N=XX)
MAXIMUM	XX	XX	XX
STRATIFICATION n, (%)			
MALE, SMOKER, BASELINE MGI ≤ 2.0	xx (xx.x)	xx (xx.x)	xx (xx.x)
MALE, SMOKER, BASELINE MGI > 2.0	xx (xx.x)	xx (xx.x)	xx (xx.x)
MALE, NON-SMOKER, BASELINE MGI ≤ 2.0	xx (xx.x)	xx (xx.x)	xx (xx.x)
MALE, NON-SMOKER, BASELINE MGI > 2.0	xx (xx.x)	xx (xx.x)	xx (xx.x)
FEMALE, SMOKER, BASELINE MGI ≤ 2.0	xx (xx.x)	xx (xx.x)	xx (xx.x)
FEMALE, SMOKER, BASELINE MGI > 2.0	xx (xx.x)	xx (xx.x)	xx (xx.x)
FEMALE, NON-SMOKER, BASELINE MGI ≤ 2.0	xx (xx.x)	xx (xx.x)	xx (xx.x)
FEMALE, NON-SMOKER, BASELINE MGI > 2.0	xx (xx.x)	xx (xx.x)	xx (xx.x)

Page x of y

PPD

Protocol 207014

Program Run Date:xxxx

Table 14.2.1.1
Statistical Analysis of Bleeding Index Score
Intent-to-Treat Population

Intent-to-Treat Population (N=XX)

Visit		Test Dentifrice (N=XX)		Reference Dentifrice (N=XX)	
Week 6	LSmean (SE) [1]	x.xx (x.xxx)		x.xx (x.xxx)	
	Comparison [1][2]	Difference	95% CI	P-value	%Diff[3]
	Test Dentifrice vs Reference Dentifrice	x.xx	(x.xx, x.xx)	0.xxxx	xx.x
Week 12	Same as above				

[1] From ANCOVA with treatment, gender, smoking status and baseline MGI stratification as factors and baseline as covariate.

[2] Difference is the first named treatment minus second named treatment such that a negative difference favors the first named treatment.

[3] Percentage difference calculated as (treatment difference/adjusted mean of reference treatment)*100%.

PPD

Programming Note: For Table 14.2.3.2, please update footnote [1] as

[1] From ANCOVA with treatment, gender, smoking status as factors and baseline as covariate.

Protocol 207014

Program Run Date:xxxx

Table 14.2.1.2
Summary of Bleeding Index Score
Intent-to-Treat Population

Intent-to-Treat Population (N=XX)

Visit		Test Dentifrice (N=XX)	Reference Dentifrice (N=XX)	Overall (N=XXX)
Baseline	n	Xx	xx	xx
	MEAN	x.xx	x.xx	x.xx
	SD	x.xxx	x.xxx	x.xxx
	SE	x.xxx	x.xxx	x.xxx
	MEDIAN	x.xx	x.xx	x.xx
	MINIMUM	X.xx	x.xx	x.xx
	MaxIMUM	X.xx	x.xx	x.xx
Week 6	n	Xx	xx	
	MEAN	x.xx	x.xx	
	SD	x.xxx	x.xxx	
	SE	x.xxx	x.xxx	
	MEDIAN	x.x	x.x	
	MINIMUM	X.x	x.x	
	MAXIMUM	X.x	x.x	
Week 12	Same as above			

Protocol 207014

Program Run Date:xxxx

Table 14.2.6
 Repeatability for Modified Gingival Index
 Repeatability Population

Repeatability Population (N=XX)

	Repeated	Missing	0	1	2	3	4
Initial							
Missing		xx	xx	xx	xx	xx	xx
0		xx	xx	xx	xx	xx	xx
1		xx	xx	xx	xx	xx	xx
2		xx	xx	xx	xx	xx	xx
3		xx	xx	xx	xx	xx	xx
4		xx	xx	xx	xx	xx	xx
Kappa	0.xx						
95% CI	(0.xx, 0.xx)						

MGI Score

0: Absence of inflammation; 1: Mild inflammation; slight change in color, little change in color, little change in texture of any portion of marginal or papillary gingival unit; 2: Mild inflammation; criteria as above but involving the entire marginal or papillary gingival unit; 3: Moderate inflammation; glazing, redness, edema and/or hypertrophy of marginal or papillary gingival unit; 4: Severe inflammation; marked redness, edema and/or hypertrophy of marginal or papillary gingival unit, spontaneous bleeding, congestion, or ulceration.

Programming Note: For Table 14.2.5.2, use PI score descriptions in footnote.

Oral Health

207014

Statistical Reporting and Analysis Plan Amendment 1, 19 Jan 2018

Protocol 207014

Program Run Date:xxxx

Table 14.3.1.1
Treatment Emergent Adverse Event by System Organ Class and Preferred Term
Safety Population

Safety Population (N=xx)

System Organ Class Preferred Term	Test Dentifrice (N=XX)		Reference Dentifrice (N=xx)		Overall (N=xx)	
	n (%)	nAE	n (%)	nAE	n (%)	nAE
NUMBER OF SUBJECTS WITH AT LEAST ONE TEAE	xx (xx.x)	xx	xx (xx.x)	xx	xx (xx.x)	xx
NUMBER OF SUBJECTS WITH NO TEAE	xx (xx.x)	xx	xx (xx.x)	xx	xx (xx.x)	xx
SKIN AND SUBCUTANEOUS TISSUE DISORDERS	xx (xx.x)	xx	xx (xx.x)	xx	xx (xx.x)	xx
ERYTHEMA	xx (xx.x)	xx	xx (xx.x)	xx	xx (xx.x)	xx
DERMATITIS	xx (xx.x)	xx	xx (xx.x)	xx	xx (xx.x)	xx
GASTROINTESTINAL SYSTEM	xx (xx.x)	xx	xx (xx.x)	xx	xx (xx.x)	xx
ABDOMINAL PAIN	xx (xx.x)	xx	xx (xx.x)	xx	xx (xx.x)	xx
DRY MOUTH	xx (xx.x)	xx	xx (xx.x)	xx	xx (xx.x)	xx
VOMITTING	xx (xx.x)	xx	xx (xx.x)	xx	xx (xx.x)	xx

Etc.

n (%) = Number (percent) of subjects

nAE = Number of adverse events.

[figure not shown]
Page x of y

PPD

Note to Programmer: For Table 14.3.1.2, change 'System Organ Class' to 'Oral/Non-Oral'

Figure 14.2.1
Mean Bleeding Index Score over Time
Intent-to-Treat Population

Intent-to-Treat Population (N=XX)

Mean and SE are plotted from summary statistics in T 14.2.1.2

Oral Health

207014

Statistical Reporting and Analysis Plan Amendment 1, 19 Jan 2018

Protocol 207014

Program Run Date:xxxx

Listing 16.1.7
Randomization Information
All Randomized Subjects

Study Population: All Randomized Subjects (N=XX)
Stratum 1: MALE, Smoker, BASELINE MGI ≤ 2.0

Subject Number	Age/Sex/ Race [1]	Randomization Number	Treatment Randomized	Actual Treatment Received	Date of Randomization
PPD					

[1] Age in years; Sex: F = Female, M = Male; Race: A = Asian, B = Black or African American, I = American Indian or Alaska Native, H = Native Hawaiian or Other Pacific Islander, W = White, M = Multiple

PPD

Oral Health

207014

Statistical Reporting and Analysis Plan Amendment 1, 19 Jan 2018

Protocol 207014

Program Run Date:xxxx

Listing 16.2.1.1
Subject Disposition
All Randomized Subjects

Study Population: All Randomized Subjects (N=XX)

Treatment Group: Test Dentifrice

Subject	Age/Sex/ Race [1]	Screening Date	Treatment Start Date and Time	Date of Completion or Withdrawal	Duration of Treatment (Days)	Completed	Primary Reason for Withdrawal	Further Details[2]
[REDACTED]								

PPD

[1] Age in years; Sex: F = Female, M = Male; Race: A = Asian, B = Black or African American, I = American Indian or Alaska Native, H = Native Hawaiian or Other Pacific Islander, W = White, M = Multiple.

[2] Further details of reasons for withdrawal.

Page x of y

PPD

Oral Health

207014

Statistical Reporting and Analysis Plan Amendment 1, 19 Jan 2018

Protocol 207014

Program Run Date:xxxx

Listing 16.2.1.2
Subject Disposition
Non-Randomized Subjects

Study Population: Non-Randomized Subjects (N=XX)

Subject Number	Age/Sex/ Race [1]	Screening Date	Reason for Screen Failure	Further Details[2]
PPD				

[1] Age in years; Sex: F = Female, M = Male; Race: A = Asian, B = Black or African American, I = American Indian or Alaska Native, H = Native Hawaiian or Other Pacific Islander, W = White, M = Multiple.

[2] Further details of reasons for screen failure.

Page x of y

PPD

Oral Health

207014

Statistical Reporting and Analysis Plan Amendment 1, 19 Jan 2018

Protocol 207014

Program Run Date:xxxx

Listing 16.2.2.1
Important and Major Protocol Deviations
All Randomized Subjects

Study Population: All Randomized Subjects (N=XX)

Treatment Group: Test Dentifrice

Subject	Sex/Age/ Race [1]	Week(s) Excluded from PP Population	Deviation Reason
PPD			

[1] Age in years; Sex: F = Female, M = Male; Race: A = Asian, B = Black or African American, I = American Indian or Alaska Native, H = Native Hawaiian or Other Pacific Islander, W = White, M = Multiple.

Page x of y

PPD

Oral Health

207014

Statistical Reporting and Analysis Plan Amendment 1, 19 Jan 2018

Protocol 207014

Program Run Date:xxxx

Listing 16.2.2.2
Minor Protocol Deviations
All Randomized Subjects

Study Population: All Randomized Subjects (N=XX)

Treatment Group: Test Dentifrice

Subject Number	Age/Sex/Race[1]	Visit	Deviation Sequence	Protocol Deviation
PPD				

[1] Age in years; Sex: F = Female, M = Male ; Race: A = Asian, B = Black or African American, I = American Indian or Alaska Native, H = Native Hawaiian or Other Pacific Islander, W = White, O = Multiple.

PPD

Oral Health

207014

Statistical Reporting and Analysis Plan Amendment 1, 19 Jan 2018

Protocol 207014

Program Run Date:xxxx

Listing 16.2.3.1
Exclusion from Analysis Populations
All Randomized Subjects

Study Population: All Randomized Subjects (N=XX)

Treatment Group: Test Dentifrice

Subject Number	Age/Sex/Race[1]	Treatment Start Date and Time	Randomized Population	Safety Population	ITT Population	PP population
PPD						

[1] Age in years; Sex: F = Female, M = Male ; Race: A = Asian, B = Black or African American, I = American Indian or Alaska Native, H = Native Hawaiian or Other Pacific Islander, W = White, O = Multiple.

Page x of y

PPD

Programming Note for Listing 16.2.3: This listing is based on population definition document.

Oral Health

207014

Statistical Reporting and Analysis Plan Amendment 1, 19 Jan 2018

Protocol 207014

Program Run Date:xxxx

Listing 16.2.4.1
Demographic Characteristics
All Randomized Subjects

Study Population: All Randomized Subjects (N=XX)

Treatment Group: Test Dentifrice

Subject Number	Age (years)	Sex	Race	Stratification
-------------------	-------------	-----	------	----------------

PPD

Page x of y

PPD

Oral Health

207014

Statistical Reporting and Analysis Plan Amendment 1, 19 Jan 2018

Protocol 207014

Program Run Date:xxxx

Listing 16.2.4.2
Medical History and Current Medical Conditions
All Randomized Subjects

Study Population: All Randomized Subjects (N=XX)

Treatment Group: Test Dentifrice

Subject	Age/Sex/Race	Any Medical History?	Medical Condition	Start Date	Ongoing?	End Date
PPD	[1]					

[1] Age in years; Sex: F = Female, M = Male; Race: A = Asian, B = Black or African American, I = American Indian or Alaska Native, H = Native Hawaiian or Other Pacific Islander, W = White, M = Multiple.

Page x of y

PPD

Oral Health

207014

Statistical Reporting and Analysis Plan Amendment 1, 19 Jan 2018

Protocol 207014

Program Run Date:xxxx

Listing 16.2.5.2
Concomitant Medications and Significant Non-drug Therapies Taken During Treatment
All Randomized Subjects

Study Population: All Randomized Subjects (N=XX)

Treatment Group: Test Dentifrice

Subject Number	Age/Sex/Race[1]	Sequence Number	Treatment or Drug Synonym	Reason for Treatment	Frequency	Start Date (Study Day[2])	End Date/Ongoing
----------------	-----------------	-----------------	---------------------------	----------------------	-----------	---------------------------	------------------

PPD

[1] Age in years; Sex: F = Female, M = Male; Race: A = Asian, B = Black or African American, I = American Indian or Alaska Native, H = Native Hawaiian or Other Pacific Islander, W = White, M = Multiple.

[2] Study day relative to the date of Randomization

PPD

Oral Health

207014

Statistical Reporting and Analysis Plan Amendment 1, 19 Jan 2018

Protocol 207014

Program Run Date:xxxx

Listing 16.2.6.1
Bleeding Index
All Randomized Subjects

Study Population: All Randomized Subjects (N=XX)
Treatment Group: Test Dentifrice

Subject Number	Age/Sex/Race[1]	Visit	Tooth Number (universal/FDI)	Surface	Site	Index
PPD						

[1] Age in years; Sex: F = Female, M = Male; Race: A = Asian, B = Black or African American, I = American Indian or Alaska Native, H = Native Hawaiian or Other Pacific Islander, W = White, M = Multiple.

PPD

Oral Health

207014

Statistical Reporting and Analysis Plan Amendment 1, 19 Jan 2018

Protocol 207014

Program Run Date:xxxx

Listing 16.2.6.4
Efficacy Endpoints
All Randomized Subjects

Study Population: All Randomized Subjects (N=XX)
Treatment Group: Test Dentifrice

Subject Number	Age/Sex/Race[1]	Visit	BI Score[2]	Number of Bleeding Sites[3]	MGI Score[4]	Overall PI Score[5]	Interproximal PI Score[6]
PPD							

[1] Age in years; Sex: F = Female, M = Male; Race: A = Asian, B = Black or African American, I = American Indian or Alaska Native, H = Native Hawaiian or Other Pacific Islander, W = White, M = Multiple.

[2] BI score is the average bleeding index over all tooth sites.

[3] Number of the bleeding sites is the number of sites with bleeding index of 1 or 2.

[4] MGI score is the average modified gingival index over all tooth sites.

[5] Overall PI score is the average plaque index over all tooth sites.

[6] Interproximal PI score is the average plaque index over all interproximal tooth sites.

PPD

Oral Health

207014

Statistical Reporting and Analysis Plan Amendment 1, 19 Jan 2018

Protocol 207014

Program Run Date:xxxx

Listing 16.2.7.1
All Adverse Events
All Randomized Subjects

Study Population: All Randomized Subjects (N=XX)
Treatment Group: Test Dentifrice

Subject Number	Age/Sex/Race[1]	Adverse Event (Preferred Term) [System Organ Class]	Start Date /Study Day[2]	Start Time	End Date	End Time	Frequency /Intensity [3]	Related to Study Product?	Action Taken re Study Product	Outcome	Serious?	Withdrew? [4]
----------------	-----------------	---	--------------------------	------------	----------	----------	--------------------------	---------------------------	-------------------------------	---------	----------	---------------

PPD

@@ Adverse Events with verbatim text ending in this are designated as Oral AEs.

[1] Age in years; Sex: F = Female, M = Male ; Race: A = Asian, B = Black or African American, I = American Indian or Alaska Native, H =Native Hawaiian or Other Pacific Islander, W = White, M = Multiple.

[2] Study day is the day relative to start of treatment, day 1 being the day of first treatment.

[3] INT = Intermittent and SGLE = Single.

[4] Did subject withdraw from study as a result of this adverse event?

Page x of y

PPD

